APPENDIX A. ALGORITHM FOR EVALUATING SUBJECTS FOR POTENTIAL DRUG-INDUCED LIVER INJURY

During the study, aminotransferase elevations are to be managed as follows:

1. Isolated aminotransferase elevation (i.e., total bilirubin - normal):

ALT or AST	Event during the study	Action
Baseline ALT and AST within normal range	Increase $\geq 5 \times$ ULN	Repeat liver profile (AST, ALT, bilirubin) and PT/INR within 2 to 3 business days from the date results are received for review. Monitor the subject as per “close observation” definition* in the DILI guidance.
ALT or AST above normal range at Baseline	Increase $\geq 3 \times$ Baseline result, but no liver related symptoms (e.g., anorexia, nausea, vomiting, right upper quadrant pain, pruritus, cholestasis)	Interrupt study drug for at least 15 days. Initiate potential DILI evaluation for alternative etiologies, and repeat liver profile and PT/INR within 2 to 3 business days from the date results are received for review, and place subject under “close observation” as defined in the DILI guidance.
ALT or AST above normal range at Baseline	Increase $\geq 3 \times$ Baseline result, and subject experiences liver- related symptoms (e.g., anorexia, nausea, vomiting, right upper quadrant pain, pruritus, cholestasis)	Interrupt study drug for at least 15 days. Initiate potential DILI evaluation for alternative etiologies, and repeat liver profile and PT/INR within 2 to 3 business days from the date results are received for review, and place subject under “close observation” as defined in the DILI guidance.

Abbreviations: ALP = alkaline phosphatase; ALT = alanine aminotransferase; AST = aspartate aminotransferase; DILI = drug-induced liver injury; GGT = gamma-glutamyltransferase; INR = international normalized ratio; PT = prothrombin time; ULN = upper limit of normal.

*Close observation as defined in the FDA DILI guidance (i.e., laboratory testing and physical examination 2 to 3 times per week. Study drug is to be restarted only if a firm alternative etiology is “identified” and the liver tests return to ‘baseline’ levels).

Note the following:

The ‘baseline’ result for any laboratory parameter is the average of the Screening visit result, the Day 1 visit result and any unscheduled visit that occurred during the Screening period.’

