Study drug interruption refers to cessation of study drug intake, but with the possibility that intake may re-start at a later date if certain requirements described in this appendix are confirmed.

Conversely, study drug discontinuation refers to cessation of study drug intake and without the possibility that intake may restart at a later date. However, such a subject should remain in the study, continue to undergo ‘close observation’ where required, and other scheduled study assessments.

If a subject sustains a liver test elevation but remains eligible to continue study drug intake in parallel with ‘close observation’, and ‘close observation’ is not possible then study drug intake should be interrupted until it is possible for the subject to undergo further assessment.

Close observation as defined in the FDA DILI guidance i.e., laboratory testing and physical examination 2 to 3 times per week. Study drug is to be restarted only if a firm alternative etiology is “identified” and the liver tests return to ‘baseline’ levels.

2. Elevation of aminotransferase and total bilirubin or cholestatic liver test markers:

Analyte	Event during the study	Action
TB + AST or ALT	↑ TB >2 mg/dL and ↑ ALT or ALT \geq 3 × Baseline or 5 × ULN (whichever comes first)	Interrupt study drug for at least 15 days. Initiate potential DILI evaluation for alternative etiologies. Repeat liver profile and PT/INR within 2 to 3 business days from the date results are received for review, and place subject under “close observation” as defined in the DILI guidance.
TB, ALP, or GGT	↑ TB >2 mg/dL and ALP or GGT ↑ >2 × ULN	Study drug can be re-started only if a firm competing etiology is identified and the liver tests return to Baseline levels.
TB OR INR + symptoms (regardless of any magnitude AST/ALT elevation)	Elevation ↑ TB >2 mg/dL OR INR \geq 1.5 and Indicators of immunological reaction (i.e., rash or >5% eosinophilia), or appearance of liver-related symptoms, e.g., anorexia, nausea, vomiting, right upper quadrant pain, pruritus, cholestasis.	Permanently discontinue study drug. Initiate potential DILI evaluation for alternative etiologies. Repeat liver profile and PT/INR within 2 to 3 business days from the date results were received for review, and place subject under “close observation” as defined in the DILI guidance.

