Abbreviations: ALP = alkaline phosphatase; ALT = alanine aminotransferase; AST = aspartate aminotransferase; DILI = drug-induced liver injury; GGT = gamma-glutamyltransferase; INR = international normalized ratio; PT = prothrombin time; TB = total bilirubin; ULN = upper limit of normal.

Note the following:

If a subject lives in a remote area, they can be tested using a local (‘non-central’) laboratory, with the results communicated to the Investigator promptly.

For subjects with Gilbert’s syndrome, a doubling of direct bilirubin concentration instead of total bilirubin concentration should be used for close monitoring and TVB-2640 discontinuation.

If either of the following criteria are met, study drug must be discontinued and the subject must be followed until the clinical and laboratory abnormalities stabilize or normalize:

- In the presence of total bilirubin elevation ($>2 \times$ ULN or $>1.5 \times$ Baseline level); with any degree of aminotransferase elevation; AND if there is appearance of symptoms i.e., fatigue, nausea, vomiting, right upper quadrant pain or tenderness, fever, rash, and/or eosinophilia ($>5\%$).
- If any total bilirubin, ALT, or AST elevation above the subject's Baseline result recurs following rechallenge with study drug.

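### Appendix A orders no explicit drug hold or DILI evaluation for a symptomatic subject with normal Baseline ALT and AST who reaches 5 × ULN or more, when bilirubin is not raised and INR is below 1.5

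*Protocol*

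**What the plan says.** Appendix A item 1 covers aminotransferase rises with normal total bilirubin, in three rows.

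- **Row 1.** Baseline ALT and AST both normal, rise to 5 × ULN or more. The actions are "Repeat liver profile (AST, ALT, bilirubin) and PT/INR within 2 to 3 business days from the date results are received for review" and monitoring under the close-observation "definition* in the DILI guidance". Symptoms, a hold and a DILI evaluation are not mentioned.
- **Rows 2 and 3.** ALT or AST above normal at Baseline, rise to 3 × Baseline or more, without symptoms (row 2) or with them (row 3). Both carry the same action: "Interrupt study drug for at least 15 days. Initiate potential DILI evaluation for alternative etiologies, and repeat liver profile" and PT/INR, with close observation.

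Row 1's asterisk leads to a footnote that defines close observation as tests and examination 2 to 3 times a week. It adds a restart condition: "Study drug is to be restarted only if a firm alternative etiology is" identified and liver tests are back at baseline levels. A further note in Appendix A foresees a subject who "remains eligible to continue study drug intake in parallel with" close observation, and requires interruption where such observation is not possible.

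Other rules that could apply:

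- Item 2 rows 1 and 2 need bilirubin above 2 mg/dL.
- Item 2 row 3, labelled "TB OR INR + symptoms (regardless of any magnitude AST/ALT elevation", orders permanent discontinuation when bilirubin exceeds 2 mg/dL or INR is 1.5 or more, together with liver symptoms or signs of an immunological reaction.
- The closing criteria require discontinuation when bilirubin exceeds 2 × ULN or 1.5 × Baseline "with any degree of aminotransferase elevation; AND if there is appearance of symptoms i.e., fatigue, nausea, vomiting" (among others), or when an elevation recurs after rechallenge.
- Section 8.3 sends suspected DILI to Appendix A and lets the investigator withdraw a subject for an unacceptable AE. Section 7.3 permits dose interruptions.

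**The concern.** Within item 1, the subject with the larger relative rise gets the weaker written instruction. A raised-Baseline subject without symptoms must be held and evaluated at 3 × Baseline. A normal-Baseline subject with nausea or right upper quadrant pain at 5 × ULN or more need only be retested and watched. Exclusion 12 bars ALT or AST above 5 × ULN at Screening, so this subject has reached about the level that would have kept them out of the trial.

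With approximately 100 centers, two sites can read the same row and act differently, one holding drug and the other continuing. Such subjects can enrol: inclusion 8 asks only for AST above 20 U/L, and no ALT minimum is set. What is at stake is subject safety and consistent handling across sites. The primary analysis is affected only slightly.

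**Working it through.** No sample size, power or alpha figure is involved, so there is no plan figure to reproduce. Thresholds come from Appendix A and the dose from Section 9.5. The documents give no ULN and no Baseline distribution, so the ULN values and individual results below are assumptions.

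**1. Size of rise at each trigger.** For a normal Baseline b ≤ ULN, row 1 triggers at a fold-rise of 5 × ULN / b ≥ 5.0. Rows 2 and 3 trigger at 3.0. With ULN 30, 40 or 50 U/L, row 1 triggers at 150, 200 or 250 U/L.

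In absolute terms the raised-Baseline trigger is lower only if 3b < 5 × ULN, that is b < 5/3 = 1.67 × ULN. At b = 80 U/L with ULN 40 it is 3 × 80 = 240 U/L, or 240/40 = 6 × ULN. So the contrast in fold-rise always holds, but the contrast in absolute level does not.

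**2. Two subjects (ULN 40 U/L, first rise, INR 1.1, bilirubin 0.5 rising to 0.6 mg/dL).**

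| Subject | Baseline → peak ALT | × ULN | × Baseline | Symptoms | Row | Hold and DILI evaluation ordered? |
|---|---|---|---|---|---|---|
| A | 38 → 400 | 400/40 = 10 | 400/38 = 10.5 | Nausea | 1 | No |
| B | 44 → 132 | 132/40 = 3.3 | 132/44 = 3.0 | None | 2 | Yes, at least 15 days |

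The ordering is the same when both have symptoms. Baseline 0.9 × ULN rising to 8 × ULN (8.9-fold) falls under row 1, with no ordered hold. Baseline 1.1 × ULN rising to 4.9 × ULN (4.5-fold) falls under row 3 and is held.

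**3. Does any other rule stop drug for subject A?**

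- Item 2 rows 1 and 2: bilirubin must exceed 2 mg/dL; it is 0.6. No.
- Item 2 row 3: bilirubin above 2 mg/dL or INR of 1.5 or more; the values are 0.6 and 1.1. No.
- Closing criteria, bilirubin: 1.5 × 0.5 = 0.75 mg/dL is not exceeded (0.6/0.5 = 1.2), and bilirubin is normal, so 2 × ULN is not reached. No. Above 0.75 mg/dL the answer would be yes, so the gap requires bilirubin not raised against the subject's own Baseline.
- Closing criteria, rechallenge: this is a first rise. No.
- Close observation not possible: assumed feasible. No.
- Section 8.3, suspected DILI: refers back to Appendix A. The remaining powers in Sections 7.3 and 8.3 are discretionary.

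**4. Extra exposure against row 3's minimum hold.** If drug is stopped at the repeat test, 2 to 3 business days are 2 to 5 calendar days: 2 to 5 doses × 50 mg = 100 to 250 mg. If it is not stopped at all over the 15 days: 15 × 50 = 750 mg. Close observation over 15/7 = 2.14 weeks gives 2.14 × 2 = 4.3 to 2.14 × 3 = 6.4, about 4 to 6 visits.

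**5. Effect of the added row.** Subject A moves from retest and observation to hold, DILI evaluation, retest and observation. Two groups are unchanged. Asymptomatic normal-Baseline subjects at 5 × ULN or more stay on row 1. Symptomatic normal-Baseline subjects below 5 × ULN still meet no item 1 row: for example, 38 → 190 U/L is 190/38 = 5.0 × Baseline but 190/40 = 4.75 × ULN.

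**The case against.** The best defence is that row 1 is not silent. Its asterisk attaches a restart condition and a search for another etiology, and both presuppose a stop and an evaluation. The appendix is itself titled as an algorithm for evaluating potential DILI. Row 1 points to outside DILI guidance and Section 8.3 to the Study Manual, neither of which was available here. Resuming drug after an AE hold needs consultation with the Medical Monitor and the sponsor's Chief Medical Officer (Section 7.3). Rows 2 and 3 prescribe the same action, so symptoms do not change management for raised Baselines, and a symptom split for normal Baselines could be called preference.

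Much of this stands, and it limits the point to the protocol text. It does not close the gap. A restart condition orders no stop. The note on dosing under close observation foresees continued treatment, and row 1 is the only item 1 row without a hold. The consultation rule governs resumption, not the decision to hold. A later trigger for normal Baselines may be deliberate, but that does not explain a lighter action once it is reached with symptoms.

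Two stronger readings are tempting, and the documents support neither. A reader might infer that the appendix directs dosing to continue; it is unclear, not plainly permissive. A reader might also take item 2 row 1, triggered at 3 × "Baseline or 5 × ULN (whichever comes first", to mean that subject A with bilirubin above 2 mg/dL would merely be held, from 3 × 38 = 114 U/L. Because subject A has nausea, item 2 row 3 and the closing criteria apply, and both require permanent discontinuation. The protocol is strict on symptoms with raised bilirubin or INR.

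**Conclusion.** The point holds in a narrow form and should be fixed. No rule in the protocol mandates a hold or DILI evaluation for a first, symptomatic rise to 5 × ULN or more from normal Baseline ALT and AST, with bilirubin not raised, INR below 1.5 and close observation feasible. Following row 1 as written can keep such a subject on drug. Per subject the extra exposure is at most 15 doses (750 mg) against a 15-day hold, under retesting and about 4 to 6 observation visits.

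The number of subjects affected cannot be derived from the documents and is probably small. Confidence is medium, because the Study Manual or the cited guidance may say more. The worked values rest on an assumed ULN of 40 U/L, but the 5.0 against 3.0 fold-rise comparison does not depend on the ULN.

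**What to change.** Amend Appendix A item 1 in two places.

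- Limit row 1 to subjects without liver-related symptoms, so that the rows do not overlap.
- Add a row: Baseline ALT and AST within normal range, rise to 5 × ULN or more, with liver-related symptoms (row 3's list). Use row 3's action: interrupt drug for at least 15 days, start the DILI evaluation, repeat liver profile and PT/INR within 2 to 3 business days, and place under close observation.

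State openly that asymptomatic normal-Baseline subjects at 5 × ULN or more, and symptomatic ones below 5 × ULN, still have no ordered hold in item 1, and whether that is intended.

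The cost is an amendment to one table and a few more holds. Some may become permanent, because restart needs an identified alternative etiology and liver tests back at baseline. A hold beyond 15 days also lets the investigator withdraw the subject (Section 8.3), a tension that the new row inherits from row 3. Discontinuation before Week 42 counts as non-response (Section 13.2.1). Each subject lost this way who would have responded lowers the arm's response rate by 1/108 = 0.9 percentage points (TVB-2640) or 1/54 = 1.9 (placebo).

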- m. Baseline eye examinations may be performed at any time during the Screening period. Eye exams at Week 4, Week 8, Week 13, Week 26, Week 39, Week 52, Week 56 and/or Early Termination are required only if eye-related signs or symptoms are reported by the subject or observed by the investigator. If a subject experiences a treatment-emergent eye abnormality, an eye examination inclusive of slit lamp and near and far visual acuity testing should be performed by a qualified ophthalmologist or optometrist within 24 to 48 hours of event onset or on the next business day after symptom onset to evaluate the abnormality.
- n. Hematology and coagulation parameters include hemoglobin, MCV, MCHC, hematocrit, platelet count, RBC count, WBC count with differential, ANC, and PT, aPTT, INR, and fibrinogen. See also [Table 5](#).
- o. Liver aminotransferases include AST and ALT. Liver aminotransferases collected as part of the clinical chemistry panel for safety are also applicable for efficacy assessments.
- p. Fasting clinical chemistries include chloride, carbon dioxide, sodium, potassium, glucose, BUN, calcium, magnesium, creatinine, albumin, ALT, AST, ALP, GGT, total bilirubin, indirect and direct bilirubin, and total protein. CPK (total and fractionated) is to be reported at Screening and at Baseline. See also [Table 5](#).
- q. Urinalysis includes specific gravity, pH, blood, glucose, protein, ketones, and microscopic examination of sediment, if present. See also [Table 5](#).
- r. Subject contact to reliably assess medication use between visits is encouraged around Week 10, Week 17, Week 23, Week 30, Week 34, Week 43, and Week 47. See Section 9.7 for a list of accepted and excluded concomitant medications. If a subject receives a vaccine, including the COVID-19 vaccine, details regarding that vaccine should be recorded as a concomitant medication(s), including manufacturer, dose, and dates of each injection. Any vaccine-related reactions should be recorded as described in Section 12.2.
- s. The same biopsy samples will be used for histology analysis by the central study pathologist and by digital pathology.

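### Appendix A's trigger for combined bilirubin and aminotransferase elevation names ALT twice and omits AST, contradicting its own row label

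*Protocol*

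**What the plan says.** Protocol Section 8.3 directs that study drug in suspected DILI be managed by the circumstances set out in Appendix A, so the appendix is the operative rule. It opens with "During the study, aminotransferase elevations are to be managed as follows" and has two tables and a short set of closing criteria.

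- Item 1 is headed "Isolated aminotransferase elevation (i.e., total bilirubin - normal"). Its rows refer to both enzymes, for example "Baseline ALT and AST within normal range" and "ALT or AST above normal range at Baseline".
- Item 2 is headed "Elevation of aminotransferase and total bilirubin or cholestatic liver test markers". In row 1 the analyte column pairs total bilirubin with AST or ALT. The event column reads "TB >2 mg/dL and ↑ ALT or ALT", at or above 3 × Baseline or 5 × ULN, whichever is reached first. The action is to interrupt study drug for at least 15 days, start a DILI evaluation for other causes, repeat the liver tests and place the subject under close observation.

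The Schedule of Assessments (Table 2, footnote o) states: "Liver aminotransferases include AST and ALT".

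**The concern.** The label and the trigger of the same row disagree about which enzymes count. The event column is the part a site applies to a laboratory result, and there AST does not appear. A choice between ALT and ALT has no meaning, so this is an error and not a deliberate ALT-only rule.

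At stake is a drug-interruption rule in a study planned for about 100 centers. If a site applied the event cell as printed, a subject with raised bilirubin and an AST-only rise could stay on drug without the evaluation that the row exists to order. The primary and secondary efficacy analyses, the sample size and the significance level are not involved.

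**Working it through.** No arithmetic model applies. The check has three parts.

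**1. What the rest of Appendix A does.** The places that name AST, ALT or both, leaving out the abbreviation lists, are:

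1. Item 1, column heading: both.
2. Item 1, row 1, analyte ("Baseline ALT and AST within normal range"): both.
3. Item 1, row 1, action ("Repeat liver profile (AST, ALT, bilirubin"): both.
4. Item 1, row 2, analyte: both.
5. Item 1, row 3, analyte: both.
6. Item 2, row 1, label: both.
7. Item 2, row 1, event ("TB >2 mg/dL and ↑ ALT or ALT"): **ALT only**.
8. Item 2, row 3, label: both.
9. Closing criterion on rechallenge: both.

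Both enzymes are named in 8 of 9 places. The only exception is the cell that sets the trigger.

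**2. Whether another rule covers the omitted case.** Take a subject without symptoms or immunological signs who has total bilirubin above 2 mg/dL, AST at or above the row 1 threshold, ALT below it, and neither ALP nor GGT above 2 × ULN. Read row 1 by its event cell alone.

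- Item 1: does not apply, because it is limited to normal bilirubin.
- Item 2, row 1: not met, because ALT is below the threshold.
- Item 2, row 2: not met, because it needs ALP or GGT above 2 × ULN.
- Item 2, row 3: not met on its label, which requires symptoms in addition to the bilirubin or INR finding.
- First closing criterion: not met. It accepts any degree of aminotransferase elevation with raised bilirubin, but also requires symptoms or signs such as fever, rash or eosinophilia.
- Second closing criterion: not met, because it concerns recurrence after rechallenge.

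So no row or closing criterion orders interruption or a DILI evaluation for this subject. Read by its label, row 1 does.

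**3. Whether the literal result makes sense.** Suppose this subject's AST was above normal at Baseline and has risen to at least 3 × Baseline. With normal bilirubin, item 1, row 2 orders interruption and a DILI evaluation. With bilirubin above 2 mg/dL, the literal event cell orders neither. The more worrying picture would get the weaker response, which confirms that the cell is not what was meant.

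**The case against.** The strongest reply is that this is a typing slip that corrects itself. The label, the item heading, the appendix's opening sentence and the definition in Table 2 all supply AST, and few investigators would be misled. That stands, and it is why the practical risk is rated small.

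A second reply is that the gap depends on ignoring the label in row 1 while relying on it in row 3. The event cell of row 3 joins its conditions with an ambiguous mix of OR and AND. It could be parsed so that bilirubin above 2 mg/dL alone leads to permanent discontinuation and a DILI evaluation, which would cover the subject above. The gap does depend on how row 3 is read, but that parse is not tenable. It would make rows 1 and 2 pointless, since both already require bilirubin above 2 mg/dL and lead only to interruption with possible restart. It also contradicts row 3's own label.

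Third, other text softens the consequence. Section 12.1.5 makes clinically significant laboratory abnormalities reportable as adverse events and allows repeat testing. Section 8.3 lets the investigator withdraw a subject for an unacceptable adverse event and refers sites to a Study Manual that is not among the documents. Appendix A calls for interruption when close observation is required but not possible. These make a missed work-up less likely, but none of the provisions available for review restates the row 1 trigger.

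Finally, the table was read from PDF by a program, and the action cell of row 2 looks split. A misread letter cannot be excluded, although the label in the same row was read as AST. This stands as a limit on the finding.

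**Conclusion.** The concern holds. On the supplied text the trigger is wrong as written: it omits AST where the row's own label includes it, in a rule that Section 8.3 makes operative. AST was clearly intended. The literal coverage gap is confined to asymptomatic subjects with bilirubin above 2 mg/dL, an AST-only rise over the threshold, and neither ALP nor GGT above 2 × ULN.

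The practical severity is low. The documents give no frequency for this pattern, so no number of affected subjects is claimed, and efficacy conclusions are unaffected. The finding assumes that the cell was read correctly from the PDF and that row 3 is governed by its label. Confidence is medium because the source PDF has not been seen. The correction is still worth making: a safety trigger should not depend on each site repairing it by inference.

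**What to change.** Check the cell in the source PDF first. If it reads as shown here, replace the first ALT with AST, so that the event becomes total bilirubin above 2 mg/dL together with AST or ALT at or above 3 × Baseline or 5 × ULN, whichever comes first. Nothing else in the row needs to change.

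If subjects are still being dosed, send sites a short notice. The synopsis estimates the last subject's completion as September 2023, so dosing may already have ended. In that case, correct the table before it is reused in another protocol. The cost is one check, one word and, at most, one site notice.

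### Protocol Appendix A assigns one subject both an interruption and a permanent stop of study drug, and does not say which rule prevails

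*Protocol*

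**What the plan says.** Protocol Section 8.3 sends suspected drug-induced liver injury to Appendix A. The appendix has two numbered items, each a table, followed by notes and two closing criteria. They are called item 1 and item 2 here, because the protocol's own Tables 1 and 2 are something else.

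- **Definitions (notes between the tables).** Interruption leaves restart open if conditions in the appendix are met. Discontinuation rules restart out.
- **Item 1.** Its scope is "Isolated aminotransferase elevation (i.e., total bilirubin - normal". Row 3 applies to ALT or AST above normal at Baseline that has risen to at least 3 × the "Baseline result, and subject experiences liver- related symptoms". The action is "Interrupt study drug for at least 15 days. Initiate potential DILI evaluation for alternative etiologies, and repeat liver profile and PT/INR". Row 2, the same rise without symptoms, has the same action.
- **Item 2.** Row 1 combines bilirubin above 2 mg/dL with aminotransferase at "3 × Baseline or 5 × ULN (whichever comes first"; the action is interruption. Row 3 is labelled "TB OR INR + symptoms (regardless of any magnitude AST/ALT elevation". It needs bilirubin above 2 mg/dL or INR of at least 1.5, plus liver symptoms, rash or eosinophilia; the action is "Permanently discontinue study drug".
- **Closing criteria.** They begin "If either of the following criteria are met, study drug must be discontinued and the subject must be followed". The first needs bilirubin above 2 × ULN or above 1.5 × Baseline, any aminotransferase elevation, and symptoms. The second is a bilirubin, ALT or AST elevation above Baseline that recurs after rechallenge.

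Nothing in the appendix says which rule applies when more than one is met.

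**The concern.** Bilirubin can rise by more than half and still be normal. Such a subject stays within item 1 and at the same time meets the bilirubin limb of the first closing criterion. If that subject also has the item 1 aminotransferase rise and nausea, one rule permits restart and the other forbids it. A site that stops at the matching table row would interrupt. A site that reads to the end would discontinue.

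Two things are at stake. Subjects with the same findings could be managed differently under a liver-safety rule. The difference can also reach the primary analysis: under Protocol Section 13.2.1 and SAP Sections 7.11 and 9.1.1, a subject who stops treatment before Week 42 is scored a non-responder. A subject who is interrupted and restarts may still be scored on the biopsy.

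**Working it through.** The point is one of rule consistency, and the plan states no figure to reproduce. The check sets the rules side by side and runs constructed subjects through them.

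**Inputs**
- Triggers and actions: Appendix A, as above.
- Screening bilirubin limit of 1.3 mg/dL for subjects without Gilbert's syndrome: Protocol Section 8.2, criterion 14.
- Baseline: Appendix A uses the average of the Screening, Day 1 and any unscheduled Screening-period results.
- Bilirubin ULN: not in the documents; assumed to be 1.0 to 1.3 mg/dL.
- ALT ULN of 40 U/L: illustrative.

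**Main case.** Bilirubin 0.4 to 0.7 mg/dL, ALT 60 to 190 U/L, nausea.
- Bilirubin is normal: 0.7 is below 1.0 to 1.3.
- ALT was raised at Baseline (60 > 40) and has risen 190 / 60 = 3.17-fold, at least 3. With nausea, item 1 row 3 is met: **interrupt**.
- Bilirubin ratio: 0.7 / 0.4 = 1.75, above 1.5. Aminotransferase is elevated and nausea is on the closing list. The first closing criterion is met: **must be discontinued**.

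**Where this overlap can occur.** Bilirubin can be normal and above 1.5 × Baseline only if 1.5 × Baseline < ULN, that is, Baseline < ULN / 1.5. This is 1.0 / 1.5 = 0.67 mg/dL at the low end of the assumed ULN and 1.3 / 1.5 = 0.87 mg/dL at the high end.

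**Bilirubin triggers on one scale**

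| Source | Trigger | mg/dL |
|---|---|---|
| Item 2, rows 1 to 3 | absolute | > 2 |
| Closing criterion 1 | > 2 × ULN | > 2.0 to > 2.6 |
| Closing criterion 1 | > 1.5 × Baseline, Baseline 0.3 / 0.5 / 0.7 / 1.0 / 1.3 | > 0.45 / 0.75 / 1.05 / 1.5 / 1.95 |

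When the averaged Baseline is at or below 1.3 mg/dL, 1.5 × Baseline is at most 1.95. Any bilirubin above 2 mg/dL then also exceeds 1.5 × Baseline, but the reverse is not true. INR appears only in item 2.

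**Symptom lists.** Nausea, vomiting, right upper quadrant pain, rash and eosinophilia above 5% are common to item 2 row 3 and the closing criterion. Fatigue and fever are named only in the closing list. Anorexia, pruritus and cholestasis are named only in the tables.

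**Further checks**
- Bilirubin 0.8 to 2.3 mg/dL, ALT 60 to 190 U/L, nausea: item 2 row 1 says interrupt; row 3 of the same table and the first closing criterion (2.3 / 0.8 = 2.88) say discontinue.
- ALT again at least 3 × a raised Baseline after rechallenge, bilirubin normal, no symptoms: item 1 row 2 says interrupt; the second closing criterion says discontinue.
- Bilirubin 0.8 to 2.3 mg/dL, ALT 60 to 190 U/L, no symptoms, no rechallenge: interruption only.

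The overlap therefore needs symptoms or a recurrence after rechallenge. The further checks gave the same results at assumed ULNs of 1.0, 1.2 and 1.3 mg/dL, and the main case holds for any ULN of 0.7 mg/dL or more.

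**The case against.** The best reply is that the closing criteria are an override. They come after both tables, are not limited to either, and are worded as mandatory. Interruption is defined as leaving restart open only under conditions found in the appendix, and these criteria are in the appendix. The second one makes most sense as a limit on an earlier interruption. On this reading the drug stops under either rule, and the closing criteria settle only whether it may be restarted. Restart after an interruption is in any case tightly conditioned: another cause must be firmly established and liver tests must be back at Baseline.

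This is a plausible reading, and it limits the practical gap to subjects who would otherwise qualify for restart. But it is not written down. Nor does it explain why item 1 separates subjects with and without symptoms and then gives both the same action.

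A reader might infer more than the documents support:
- **That item 2 row 3 contradicts the closing criteria on action.** It does not. Both end in permanent discontinuation, and two triggers for one action can work as alternatives. Their symptom lists also overlap substantially, and the symptom part of the item 2 list is given as examples only. What is missing is a statement of how the two relate.
- **That the rules must share one bilirubin scale and one symptom list.** Absolute and relative triggers can coexist; that choice is clinical.
- **That the item 1 row for normal Baseline and at least 5 × ULN is defective because it names no interruption.** The notes provide for continued dosing under close observation, and for interruption when such observation is not possible.
- **That AST has been lost from item 2 row 1, whose trigger names ALT twice.** The row label names both enzymes, so this is a typing error.

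**Conclusion.** The concern holds in a limited form. Read as written, item 1 row 3 and the first closing criterion give the same subject two mutually exclusive instructions, and no order of precedence is stated. The difference in bilirubin triggers and symptom lists between item 2 and the closing criteria is an unexplained relation, not a second contradiction in action.

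Its size cannot be put as a number of subjects, because the documents give no rate for this combination of findings. The affected group is narrow. In the main case it needs a raised Baseline aminotransferase, a rise to at least 3 × Baseline, symptoms on both lists, and bilirubin above 1.5 × Baseline but still normal. Subjects with Gilbert's syndrome have a separate direct-bilirubin rule and are outside the comparison. The effect on the primary endpoint arises only if sites take different readings before Week 42 for a subject who could otherwise have restarted. The example assumes a bilirubin ULN of at least 0.7 mg/dL.

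The point should be corrected because it concerns liver safety and is cheap to resolve. It does not call the trial's design or sample size into question.

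**What to change.** The sponsor should reconcile item 1, item 2 and the closing criteria of Appendix A and add a sentence stating which rule prevails when a subject meets more than one. The same text should say how the bilirubin triggers and symptom lists of item 2 and the closing criteria relate to each other. Which threshold and which action apply is for the sponsor's clinicians. As an editorial correction, the trigger in item 2 row 1 should be made to match its row label.

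The cost is a protocol clarification. If it is issued as an amendment, it goes to the ethics committees as Protocol Section 14.2 requires. No change to the sample size, visit schedule or SAP methods follows from it.
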